8.4. Prior and Concomitant Medications, Procedures and Surgeries

Prior medications are defined as medications started within 4 weeks of the screening visit up to the start of study drug, and ended prior to Study Day 1. Concomitant medications are defined as medications administered during the patient's participation in the study from informed consent date until Day 60; that is, the time between start and/or stop date of the concomitant medication includes any time from screening to Study Day 60. The same concept applies to procedures and surgeries to determine which are prior or concomitant.

Prior and concomitant medications will be summarized by treatment group for the FAS. As selected COVID-19 standard of care may begin prior to patient's informed consent, all prior and concomitant medications will be included.

Frequency summaries of coded prior and concomitant medications will be provided for each drug class and preferred base term by treatment group separately for selected COVID-19 standard of care medications and all non-COVID-19 medications. In order to ensure consistency across sites, all recorded medications will be reviewed in a blinded fashion by the study team to determine which are considered selected standard of care for COVID-19. This determination will be provided to the data management/statistical team.

At each level of summarization, each patient will be counted once if they reported one or more medications. A prior and concomitant medication listing, including randomization and treatment, and a flag for selected COVID-19 standard of care medications, reason for use, duration, frequency, route, and dosage will be provided.

Prior and concomitant procedures and surgeries will be summarized by treatment group for the FAS.

All prior and concomitant procedures and surgeries will be listed by patient for the FAS with an indication of randomization, treatment, and procedure/surgery indication.

8.5. Medical History

Baseline medical history data (including preexisting conditions) will be summarized using frequency tabulations by the Medical Dictionary for Regulatory Activities (MedDRA) system organ class (SOC) and preferred term (PT) for the FAS. Each patient will only be counted once per SOC and once per PT. Patient level listings will also be provided for the FAS with any missing or partial dates presented as shown in the study data.

8.6. Intercurrent Events

Intercurrent events such as early discontinuation of treatment, any treatment crossover, any major protocol deviations (see [Section 8.2](#)), and any other approved or authorized treatments to prevent progression of COVID-19 disease severity or to treat COVID-19 (such as monoclonal antibodies, antivirals such as remdesivir, etc.) will be tabulated by treatment group for the FAS. Patient level listings will also be provided for the FAS.

9. ASSESSMENT OF EFFICACY

Efficacy endpoints will include need for emergency room visit or hospitalization, death, the NIAID ordinal scale, and evaluation of symptoms using symptom score and patient global impression questionnaires ([Section 2](#)).

9.1. Analysis of Primary Outcome Measure

Primary efficacy analysis will be done using the FAS. The primary endpoint is the proportion of patients who experience any emergency room (ER) visit, hospitalization, or death by Day 28. Any occurrence of any of the 3 types of events as recorded on the Hospitalization (with healthcare type marked as emergency room, hospitalization, or intensive care unit (ICU)) or Death eCRFs will be considered an event, and each patient will only contribute one event to the analysis. Duration of ER visit and hospitalization stay (including any ICU stay) based on duration < 24hrs or \geq 24 hrs will be tabulated separately. Stays in extended care facilities will also be recorded on the eCRFs but these will not count towards the primary endpoint. It is assumed that a stay in such a facility would follow a hospitalization and that hospitalization would count toward the endpoint. Any responses of “other” to the healthcare type will be reviewed and categorized by the study team prior to unblinding. Any patient in the FAS that is lost to follow-up prior to Day 28, such that determination of ER visit, hospitalization or death cannot be made, will be considered as no event in the primary analysis.

Statistical hypothesis testing for the primary endpoint will be conducted using a logistic regression model with a Firth penalized likelihood (Firth, 1993) at the two-sided 0.05 significance level. The model will include treatment as the independent variable. Event rates within strata will be evaluated to determine whether it is appropriate to conduct a sensitivity analysis that includes stratification by the randomization stratification factors for geographic region (US vs outside US) and completion of a COVID-19 vaccination regimen or participation in a COVID-19 vaccine clinical trial (yes, no). This analysis may include an exact conditional logistic regression with stratification by appropriate variables or other similar methodology. Based on the observed event rates within strata, the decision whether to conduct this stratified sensitivity analysis and the methodology to be used will be made prior to any unblinding of the study team and documented in the final study report.

The primary estimand of treatment effect will be the risk difference between treatment arms, corresponding 95% confidence interval (CI), and p-value based on a Wald test. The confidence interval for the risk difference will be obtained using the delta method. Additionally, the odds ratio, corresponding 95% CI, and p-value will be generated.

The proportion of patients who have any ER visit, hospitalization, or death by Days 7, 14 and 28, and at any time during the study (e.g., to Day 60) will be tabulated. A Chi-square or Fisher’s exact test will compare treatment arms at each timepoint of interest. Number and percentage of patients who experience each type of healthcare as listed on the Hospitalization eCRF will also be tabulated by treatment arm.

Individual data listings of ER visits, hospitalizations, or deaths will be provided with an indication of whether or not the event occurred by Day 28 and whether or not the event was COVID-19-related, along with treatment arm, randomization strata, age, race, and sex for each patient.

Two sensitivity analyses will be conducted mirroring primary endpoint analysis methods as specified above.

1. The first sensitivity analysis will define the endpoint as any COVID-19-related emergency room visits, COVID-19-related hospitalizations, or deaths (any cause).
2. The second sensitivity analysis will define the endpoint the same way as the primary analysis, but will be conducted using the mITT Population.

A third sensitivity analysis will be conducted if the primary endpoint is missing for 5% or more of patients; i.e., missing the primary endpoint, in this case, refers to patients who were not followed through Day 28, and were not known to have an ER visit, hospitalization, or death. This analysis will use a multiple imputation approach (such as Marcov Chain Monte Carlo method, or FCS method with logistic regression) to impute missing values for patients who are missing the primary endpoint due to loss to follow-up or discontinuation prior to Day 28 (Little 2019). Covariates to consider when imputing the missing data will at a minimum include treatment arm, and those listed in [Section 12.1](#).

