3. STUDY DESIGN AND PROCEDURES

This Phase 2b study will randomize approximately 500 patients who are symptomatic with mild or moderate COVID-19 who are at high risk for progression to more severe disease. Patients will be randomized in a 1:1 ratio to 250 mcg of inhaled sargramostim plus SOC or equivalent volume of placebo diluent plus SOC. Randomization will be stratified by geographic region (US, outside the US), and by completion of a COVID-19 vaccination regimen or participation in a COVID-19 vaccine clinical trial (yes, no). Enrollment of patients who have completed a COVID-19 vaccination regimen or participated in a COVID-19 vaccine clinical trial will be capped at approximately 100 patients.

Treatment will be administered once daily for 5 days and delivered via a vibrating mesh nebulizer. Additional blood samples will be collected for biomarker assays for approximately 100 randomized patients (approximately 50 from each treatment group). Patients will be followed for up to 60 days after start of treatment.

Refer to protocol sections 9 and 11 for a complete description of study visits and procedures along with a schedule of events.

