4. GENERAL ANALYTIC CONSIDERATIONS

4.1. Study Size and Power

A total of approximately 500 patients will be randomized using a 1:1 assignment ratio. The sample size is selected to achieve at least 80% power to detect a difference at the 0.05 level of significance (2-sided) in the proportion of patients who experience any emergency room visit or hospitalization, or death over 28 days.

This sample size is based on an assumed 3% event rate for the sargramostim arm and a 10% rate for the placebo arm (risk ratio of 0.30) in unvaccinated patients (similar to that observed for bamlanivimab BLAZE-1 study [Chen, 2021; Gottlieb, 2021; US FDA, 2021]). As discussed in protocol Section 4.6, the rate of any emergency room visits or hospitalization, or death over 28 days is expected to be very low, or near zero for vaccinated patients.

It is also assumed that the proportion of vaccinated patients will be approximately 20-25% of the study population, with enrollment of patients who have completed a COVID-19 vaccination regimen or participated in a COVID-19 vaccine clinical trial capped at approximately 100 patients; no events are expected to occur in these patients for either treatment arm. Therefore, the overall event rate (for unvaccinated and vaccinated patients combined) for the primary endpoint is expected to be 2.4% for sargramostim and 8.0% for placebo (risk ratio of 0.30) and maintains at least 80% power.

Note that completion of a COVID-19 vaccination regimen or participation in a COVID-19 vaccine clinical trial (yes, no) is one of the randomization stratification factors (protocol Section 6.2).

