region (US vs outside US) and completion of a COVID-19 vaccination regimen or participation in a COVID-19 vaccine clinical trial (yes, no).

The primary estimand of treatment effect will be the risk difference between treatment arms, corresponding 95% confidence interval (CI), and p-value based on a Wald test. The confidence interval for the risk difference will be obtained using the delta method. Additionally, the odds ratio, corresponding 95% CI, and p-value will be generated.

The proportion of patients with any progression of disease as defined above by Days 7, 14, 28 and 60 will be tabulated. A Chi-square or Fisher's exact test will compare treatment arms at each timepoint of interest.

A sensitivity analysis will be conducted mirroring analysis methods described above but excluding any imputed scores. A repeated measures modelling approach may also be considered to utilize the available longitudinal data.

9.2.2. Time to progression of disease as determined by a \geq 2-point increase in the NIAID ordinal scale up to Day 28 and Day 60

Time to progression of disease will also be assessed. Time to progression is defined as time from randomization to first occurrence of a \geq 2-point increase in the NIAID ordinal scale up to Day 60. Patients who do not have a \geq 2-point increase in the NIAID ordinal scale by Day 60 will be censored at the date of their last non-missing NIAID assessment up to Day 60. Kaplan-Meier methods will be used for the first time to event analysis. A log rank test stratified by the 2 randomization stratification factors, as appropriate, will be used to compare the 2 treatment arms. Estimates for probability of progression at Days 7, 14, 28, and 60 days, as well as median time to progression, will be derived from Kaplan Meier analysis.

Cox's proportional hazards model stratified by the 2 randomization stratification factors, as appropriate, will also be used to derive a hazard ratio and 95% CI assessing treatment effect, along with comparisons of the timepoint estimates at Days 28 and 60, if warranted. The proportional hazards assumption necessary for both the log rank test and Cox's proportional hazards model will be assessed. Any alternative methods used will be described in the CSR.

Two sensitivity analyses will be conducted mirroring analysis methods described above:

1. Excluding any imputed scores.
2. Imputing missing data when there is no collected data, as follows:

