 - a. If there are missing scores prior to first occurrence of a \geq 2-point increase in the NIAID ordinal scale, then it will be assumed for purposes of this sensitivity analysis that the patient's score would have been equal to whatever score was recorded directly after the missing score

9.2.3. Change from baseline in overall symptom score, and individual symptom scores, as measured by the symptom score questionnaire up to Day 28

Change from baseline in the overall symptom score, and individual symptom scores from baseline to Day 28 will be analyzed using a mixed model repeated measures analysis using a missing at random assumption for handling missing data. The model will contain baseline symptom score, treatment arm, day, and treatment-by-day interaction as fixed effects, along with strata for the two randomization factors, as appropriate. The primary estimand of treatment effect

will be the treatment differences and corresponding 95% CIs, with p-values. Estimates and corresponding 95% CIs at days 7 and 14 will also be generated. Numbers and percentages of patients with each score at baseline, and days 7, 14, and 28 will also be summarized for the overall score and for each symptom by treatment arm. All available data will be used in the analysis; no imputation will be done for missing data.

The overall symptom score will be calculated as a sum of individual scores from 14 questions on the questionnaire. Each response will be scored according to the FDA's Guidance on "Assessing COVID-19-Related Symptoms in Outpatient Adult and Adolescent Subjects in Clinical Trials of Drugs and Biological Products for COVID-19 Prevention or Treatment" (US FDA, 2020). The scores correspond to the responses:

Questions 1-10: None = 0, Mild = 1, Moderate = 2, Severe = 3;

Questions 11-12: Not at all = 0, 1-2 times = 1, 3-4 times = 2, 5 or more times = 3;

Questions 13-14: Same as usual = 0, Less than usual = 1, No sense = 2.

A sensitivity analysis will be conducted mirroring the analysis methods described above but using the following assumptions:

- Completely exclude from analysis any patients who are missing more than 20% of their required symptom score questionnaires, unless the days where they are missing questionnaires fall after the patient experienced hospitalization, ER visit, or death.

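### The main analyses in SAP 9.1 and 9.2.1 omit both randomisation strata; a stratified risk difference would add about 0.8 points of power and bring size closer to 5%

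*SAP*

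**What the plan says.** SAP section 3 states: "Randomization will be stratified by geographic region (US, outside the US), and by completion of a COVID-19 vaccination regimen" (or vaccine-trial participation). Section 4.1 assumes 10% versus 3% events in unvaccinated patients; of vaccinated patients it says "no events are expected to occur in these patients for either treatment arm".

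For the primary endpoint, section 9.1 uses a Firth logistic model: "The model will include treatment as the independent variable". Section 9.2.1 specifies the same for NIAID progression. In both sections, stratification is only a possible sensitivity analysis, run or not according to event rates within strata. No criterion is given. For the primary endpoint several methods are left open, and the decision on "the methodology to be used will be made prior to any unblinding of the study team". Section 12.1 puts the strata into exploratory covariate models if numbers suffice.

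The other secondary efficacy analyses bring both factors into the main analysis, though conditionally. Section 9.2.2: "A log rank test stratified by the 2 randomization stratification factors, as appropriate, will be used". Section 9.2.3: "along with strata for the two randomization factors, as appropriate".

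On the deciding result, 9.1 names as its primary estimand "the risk difference between treatment arms, corresponding 95% confidence interval (CI), and p-value based on a Wald test", and then adds: "Additionally, the odds ratio, corresponding 95% CI, and p-value will be generated".

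**The concern.** Stratified randomisation balances a prognostic factor across arms, which lowers the true variance of the treatment comparison. A treatment-only standard error does not credit that reduction, so the test runs below its nominal level and the interval is slightly too wide. The Firth penalty, with few events, pushes the same way. Neither can produce a false positive. What is at stake is a little power that could be had almost free, and a main analysis that does not follow the randomisation scheme.

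A second loose end sits in the same paragraphs. Hypothesis testing is assigned to the logistic model, whose coefficient is a log odds ratio, while the primary estimand is the risk difference. Both get a p-value, and no sentence says which one decides.

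**Working it through.** **Inputs (SAP 4.1).** 250 per arm, two-sided 0.05. Unvaccinated: 3% versus 10%. Vaccinated: 20% of patients (the cap of about 100 in 500), no events. So each arm has 200 unvaccinated and 50 vaccinated patients, overall rates are 2.4% and 8.0%, and the true risk difference is -5.60 points.

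**1. The SAP's power figure.** The pooled SE under the null is sqrt(2 × 0.052 × 0.948 / 250) = 0.01986. The unpooled SE is sqrt((0.024 × 0.976 + 0.08 × 0.92) / 250) = 0.01970. Power = Φ((0.056 - 1.96 × 0.01986) / 0.01970) = Φ(0.867) = 80.7%. The stated figure of at least 80% reproduces.

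**2. Where the loss arises.** With arms balanced in each stratum, the Mantel-Haenszel (MH) and the crude risk difference are the same number; only the standard error differs.
- True SD: 0.8 × sqrt((0.03 × 0.97 + 0.10 × 0.90) / 200) = 1.952 points.
- Treatment-only SE: 1.970 points (step 1).
- Treatment-only Firth: p = (x + 0.5)/(n + 1). At the expected counts of 6 and 20, p = 6.5/251 = 0.0259 and 20.5/251 = 0.0817, and the delta-method SE is 2.002 points.
- MH with Sato variance, n per arm in a cell: [RD × Σ(x0 - x1)/4 + Σ(x1(n - x0) + x0(n - x1))/(4n)] / 125². At the same counts this is (-0.056 × 3.5 + 6.2)/15,625, giving an SE of 1.960 points.

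**3. Exact binomial enumeration, no regional difference.** The nulls put 10% or 6.5% in unvaccinated patients and none in vaccinated patients.

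| Risk-difference test | Power | Size, null 10% | Size, null 6.5% | Mean SE | Coverage |
|---|---|---|---|---|---|
| Planned: Firth, treatment only | 82.8% | 4.36% | 4.57% | 1.991 | 95.3% |
| Unpenalised, unstratified | 83.0% | 4.82% | 4.71% | 1.958 | 94.9% |
| MH, stratified | 83.6% | 5.07% | 5.01% | 1.949 | 94.9% |

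MH power and size are over the four region-by-vaccination cells; its SE and coverage are over vaccination status. The middle row separates the two causes:
- Power: 0.2 points from dropping Firth, 0.6 from the strata.
- Size: 0.14 to 0.46 points from Firth, 0.25 to 0.30 from the strata.
- Interval width: 1.991/1.949 is about 2.2% too wide, about 1.7 from Firth and 0.5 from the strata.

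The mean estimates are -5.58, -5.60 and -5.60 points, so bias is negligible.

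**4. Other settings (planned Firth, then MH).**
- 25% vaccinated (188 + 62 per arm): power 80.3%, then 81.1%.
- Assumed vaccinated placebo risk of 1%: 83.7%, then 84.4%; of 2%: 84.6%, then 85.2%.
- Assumed regional risk ratio of 2 (splits of 50:50 and 80:20): 82.9%, then 83.8%. Ratio of 3: 83.0-83.1%, then 84.2-84.4%; size 4.0-4.4%, then 5.0-5.1%. The SAP gives no regional rates or split.
- Without exact balance (400,000 simulated trials, assumed blocks of 4): power 82.5%, then 83.6%; size 4.38%, then 5.00%.

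**5. Adding vaccination status to the Firth model instead.** Standardising the risk difference from that model gives 83.0% power (80.4% at 25% vaccinated), a gain of only 0.1 to 0.2 points. The choice of MH therefore matters.

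**6. The two p-values as now planned.** Power is 82.8% for the risk difference and 80.8% for the odds ratio; at 25% vaccinated, 80.3% and 78.0%. They disagree in 1.9% and 2.4% of trials, always with the risk difference significant and the odds ratio not.

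No figure is possible for 9.2.1, because the SAP states no NIAID progression rate.

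**The case against.** The strongest reply is that nothing is invalid: the test is pre-specified and slightly conservative, and the risk-difference test keeps 80% power. A cautious model is understandable when one stratum is expected to have no events. A stratified sensitivity analysis is already foreseen, and for the primary endpoint the decision is taken before unblinding. Sections 9.2.2 and 9.2.3 are conditional too. All of this stands and is why the point is minor.

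It is also true that much of the conservatism is the Firth penalty. At an unvaccinated null rate of 3% the sizes (Firth, unpenalised, MH) are 4.05%, 4.83% and 4.83%; at 2% they are 3.59%, 4.47% and 4.47%. The strata add nothing there, and MH falls below 5% as well. Since 4.1.1 expects very low rates in patients given authorised therapies, such rates are plausible. MH is still nearer to nominal than the planned test.

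Two parts do not stand. A stratum without events argues for a method that tolerates it, which MH does, and not for leaving the strata out. And an optional analysis with no criterion and an open method does not replace a fixed one.

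**Conclusion.** The point holds and is minor. Under the SAP's assumptions the planned risk-difference test gives up about 0.8 points of power (0.6 from the strata, 0.2 from Firth) and runs at 4.4% to 4.6% instead of about 5%. The gain could reach about 1.3 points under an assumed regional risk ratio of 3. At very low event rates the gain in size comes from dropping Firth, not from the strata. There is no false-positive risk and no material bias.

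The undefined deciding p-value is a separate weakness that exists with or without the strata. Its effect is the larger one: a gap of about 2 points of power, and at 25% vaccinated the odds-ratio test falls below 80%.

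**What to change.** In 9.1 and 9.2.1, before unblinding:

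1. Make the main analysis an MH risk difference over the four region-by-vaccination cells, with a Sato-variance 95% CI, using the site-verified strata of 8.1. Under 1:1 allocation the weights follow stratum size, so the estimand remains the overall risk difference.
2. State that its Wald p-value alone decides the hypothesis.
3. Pool regions within vaccination status if a cell has patients in only one arm. Cells without events need no special rule.
4. Report the odds ratio, CI and p-value from a Firth model with treatment and both strata as supportive only.
5. Keep the treatment-only Firth model as a fixed sensitivity analysis, replacing the conditional rule.

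The cost is wording in two sections, one stratified procedure and a small table-shell change; no new data are needed. The sensitivity analyses that mirror 9.1, the multiple-imputation analysis and the reference to 9.1 in section 12.1 should be aligned. If the protocol prescribes the treatment-only model, section 13 needs an entry.

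### The multiple-imputation sensitivity analysis for the primary endpoint ignores time already observed event-free, so the methods it names overstate event rates; the effect on the risk difference depends on how withdrawal is split between arms

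*SAP*

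**What the plan says.** SAP Section 9.1 makes the primary endpoint a yes/no outcome by Day 28. A patient lost before Day 28 whose status cannot be determined "will be considered as no event in the primary analysis". A further sensitivity analysis, run only when at least 5% of patients lack the endpoint (25 of 500), is to "impute missing values for patients who are missing the primary endpoint due to loss to follow-up or discontinuation prior to Day 28". Missing means "patients who were not followed through Day 28, and were not known to have an ER visit, hospitalization, or death".

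The method is open-ended, with MCMC and FCS logistic regression given as examples. On the model: "Covariates to consider when imputing the missing data will at a minimum include treatment arm, and those listed in" Section 12.1. That section lists baseline characteristics and the two randomization strata, and nothing measured during follow-up. On the effect measure: "The primary estimand of treatment effect will be the risk difference between treatment arms".

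**The concern.** Everyone to be imputed was, as far as is known, event-free at last contact. A patient who has an event and then leaves is an observed event. A model for the single Day 28 outcome that uses arm and baseline factors gives a patient last seen well on Day 27 the same event probability as a similar patient lost on Day 1.

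The rate used for imputation is also too high. Patients who had an event before leaving stay among the observed, while those who left without one are removed from the denominator.

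This is the only prespecified analysis that tests the rule counting lost patients as non-events. If its event rates are biased upward, a shift in the risk difference between the two analyses cannot be read simply as the effect of relaxing that rule.

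**Working it through.** **Inputs from SAP Section 4.1.** "A total of approximately 500 patients will be randomized using a 1:1 assignment ratio", hence 250 per arm. The event rate "is expected to be 2.4% for sargramostim and 8.0% for placebo (risk ratio of 0.30"), a risk difference of 5.6 points. The target is "at least 80% power to detect a difference at the 0.05 level of significance (2-sided").

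**The plan's own figure.** With mean rate 0.052, the normal approximation gives z = [0.056 × √250 − 1.96 × √(2 × 0.052 × 0.948)] / √(0.08 × 0.92 + 0.024 × 0.976) = (0.885 − 0.615) / 0.311 = 0.87, so power is 80.7%. The stated power is reproduced.

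**Assumptions (not in the SAP).** Withdrawal is independent of outcome and uniform over Days 1–27. Event times are truncated-exponential to Day 28, with half of events by Day 7. On average, 69.8% of an arm's 28-day risk has then passed when a patient leaves (g = 0.698).

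**Formulas**, for true 28-day risk R and withdrawal proportion w:
- Rate under the primary rule: O = (1 − w)R + wRg
- Share missing: M = w(1 − Rg)
- Large-sample rate after imputation from arm-level Day 28 status: O / (1 − M)
- True remaining risk of those who leave: R(1 − g) / (1 − Rg)

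**Placebo, w = 10%.** O = 7.20 + 0.56 = 7.76%. M = 0.1 × (1 − 0.0558) = 9.44%. Imputed rate = 7.76 / 0.9056 = 8.57%. True remaining risk = 0.0242 / 0.9442 = 2.6%, against about 8.6% assigned.

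**Sargramostim, w = 10%.** O = 2.33%, M = 9.83%, imputed rate = 2.33 / 0.9017 = 2.58%.

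The risk difference is therefore 5.43 points under the primary rule, 5.60 in truth and 5.99 after imputation. The same formulas at other withdrawal rates give:

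| Withdrawal, placebo / sargramostim | Imputed placebo | Imputed sargramostim | Imputed difference | Primary-rule difference |
|---|---|---|---|---|
| 5% / 5% | 8.27% | 2.49% | 5.78 | 5.52 |
| 10% / 10% | 8.57% | 2.58% | 5.99 | 5.43 |
| 20% / 20% | 9.27% | 2.81% | 6.46 | 5.26 |
| 15% / 5% | 8.90% | 2.49% | 6.41 | 5.27 |
| 5% / 15% | 8.27% | 2.69% | 5.58 | 5.59 |
| 0% / 20% | 8.00% | 2.81% | 5.19 | 5.74 |

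In the three equal-withdrawal rows the risk ratio stays at 0.301–0.303, against a true 0.300.

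**No drug effect (8% in both arms), withdrawal 15% placebo v 5% sargramostim.** Imputation gives 8.90 − 8.27 = +0.63 points. The primary rule gives 7.64 − 7.88 = −0.24. Both signs reverse if the imbalance reverses.

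**Other timing, 10% withdrawal.** With constant hazard, placebo leavers' remaining risk is 4.2%, against 8.4% assigned, and the imputed difference is 5.9. If everyone leaves on Day 0, the bias is zero. If withdrawal falls on Days 0–5 (half of events by Day 7), the placebo rate is 8.17% after imputation and 7.37% under the primary rule.

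**Simulation** (1,200 trials, 250 per arm, 20 imputations, 10% uniform withdrawal, early events with mean 7 days). Imputation as named gave 8.67% v 2.61%, a difference of 6.06. Imputation conditional on event-free time gave 8.01% v 2.40%, a difference of 5.62. Rejection rates were 83.0% and 83.3%, against 84.0% with complete data. Under the null with equal withdrawal, both methods rejected 5.3%.

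**The case against.** **The wording is open.** The methods are examples and the covariate list is a minimum. Sections 4.5 and 5.3 leave further missing-data rules and the final imputation of endpoints to blinded review. A time-conditional imputation is therefore permitted, and a reader who infers that the SAP mandates arm and baseline factors only goes beyond the text. What stands is that nothing requires conditioning on follow-up, and both named methods, used with the minimum covariates, do not condition on it.

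**The direction is not fixed.** A reader might infer that the analysis always inflates the treatment difference. It does not: at 5% v 15% withdrawal the difference is about unbiased, and at 0% v 20% it shrinks.

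**It need not be worse than the rule it tests.** With half of events by Day 7 and uniform withdrawal, the imputed placebo rate is further from the truth (+0.57 points against −0.24). With withdrawal on Days 0–5, the ranking reverses (+0.17 against −0.63). The SAP gives neither timing.

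**Withdrawal may be informative.** If leavers' remaining risk were about 3.35 times the non-informative value (8.57 / 2.56), the imputed placebo rate would be right. A higher risk for leavers is a legitimate stress test, but it should be chosen openly and should not arise from ignoring follow-up time.

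**The effect is small.** Near the 5% trigger the difference moves by about 0.2 points, against a 95% confidence half-width of 1.96 × √(0.08 × 0.92/250 + 0.024 × 0.976/250) = 3.9 points. This is one conditional sensitivity analysis, and Section 12.2 allows others.

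**Conclusion.** The point holds in limited form. Run with the methods and minimum covariates it names, the imputation overstates the event rate in every arm with withdrawals after Day 0, provided withdrawal is non-informative. The risk difference is modestly inflated when withdrawal is similar between arms or heavier on placebo: about 0.2 points at 5% withdrawal and 0.4 at 10%, under the assumed timing. It is about unbiased or reduced when withdrawal is sufficiently heavier on sargramostim.

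A reader might infer that the analysis would make a significant result more likely. The simulation with equal withdrawal does not support that. The primary analysis itself is unaffected. The change is worth making because a better method is available at little cost, but it does not threaten the trial's main conclusion.

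**What to change.** State in Section 9.1 that the imputation conditions on the time each patient was observed event-free. Either of two forms would do:

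- Split the endpoint into first event in Days 1–7, 8–14 and 15–28, cut points that match the days Section 9.1 already tabulates. Impute sequentially within arm, only for intervals after last contact, among patients event-free at the start of each interval.
- Draw the outcome from the arm-specific Kaplan-Meier or piecewise-exponential risk between last contact and Day 28.

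Combine the results with Rubin's rules. The second form copes more easily with a patient who leaves partway through an interval, and with sparse data: 2.4% of 250 is only 6 expected events on sargramostim. Adding day of last contact as a covariate to the Day 28 model is no substitute, because everyone who completes Day 28 shares one value.

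The cost is SAP wording and slightly more programming; the event and last-contact dates are already needed for the plan's listings and tabulations. The sensitivity estimate will often be a little less favourable. The method still assumes non-informative withdrawal, and the SAP should say so.
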